http://pubs.niaaa.nih.gov/publications/Practitioner/pocketguide/pocket_guide.htm is anticipated to be implemented at all UCHC clinics beginning in 2013. We anticipate that minority patients will be represented in proportion to the general population in central Connecticut. Approximately 200 men will be enrolled with the goal of randomizing 176 to medication and that at least 160 will complete 12 weeks of treatment. Based upon our success in recruitment for a pilot study of dutasteride (C.1.c) as well as other prior ARC clinical trials involving heavy drinkers, we are confident of our ability to achieve our recruitment goal. The introduction of SBIRT at all UCHC clinical sites will provide additional assurance of our ability to accomplish our study enrollment goal. Dutasteride is not recommended for use in women due to a potential birth defect in male offspring if a woman were to become pregnant while taking the medication. We will not enroll women in the current study as the risk of giving women dutasteride for treatment of alcohol use disorders is not justified until a potential benefit in reducing heavy drinking in male subjects has been shown.

C.2.a. Temporal Sequence of Screening: Prospective participants will first undergo phone screening to assess basic inclusion / exclusion criteria. Patients who appear to be eligible will be invited for an in-person screening. After informed consent is obtained, trained study staff will obtain a brief medical history and urine and blood specimens for clinical screening as well as for genotyping the AKR1C3 H5Q polymorphism to allow balanced genotype distributions in the dutasteride and placebo treatment arms. At a subsequent baseline visit the patient will receive a physical and psychiatric examination by a study physician.

D.2.b. Criteria for Study Participation: Patients for this study are anticipated to have moderate levels of alcohol use disorder symptoms (typically meeting criteria for a diagnosis of alcohol abuse or mild to moderate AD) and want to reduce or stop their drinking. They will be asked to affirm a treatment goal of no heavy drinking days (≥ 5 standard drinks in a day).

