C.4.b. Visit 2 (Baseline Visit): 7-14 days after the screening visit, eligible subjects will return for a baseline visit where subjects will be trained to record their mood, desire to drink, self-efficacy and daily drinking using the IVR system and a physical examination will be performed by a study physician or APRN and any medication questions reviewed. Subjects will be instructed in use of study medication and given their initial 4 mg dutasteride or placebo dose and instructed to take two capsules (1 mg) daily at home for the remainder of the 12-week treatment period. Subjects will receive study medication for home use at the baseline and at each follow-up visit. At the baseline visit subjects will receive a one-week back-up supply of medication for use in case of lost capsule or need to reschedule bi-weekly follow-up visits. Subjects will be asked to bring unused medication to each follow-up visit for monitoring medication use. The UCHC research pharmacy will randomly assign subjects to dutasteride or placebo using an urn randomization to balance subjects on AKR1C3 genotype, age and baseline alcohol use. Medication will be delivered or picked up from UConn Health IDS pharmacy for distribution to patients during IDS office hours (M-F 7:30am-4pm). For IDS off-hour appointments, medication may be obtained from IDS pharmacy and kept with study staff in a locked cabinet in a locked office in preparation for that appointment. In case a patient has a last minute cancellation or is a no-show, medication can be kept with study staff until the end of the business week. If the product is not distributed to the patient during that time, it will be returned to pharmacy.

C.4.c. Bi-weekly Clinic Visits 3 - 8: A brief Timeline Follow-Back Interview will be performed to track participants' daily alcohol consumption to augment IVR reports of alcohol use (see section D.9.a.2) and a trained research staff member will deliver the medical management intervention. Blood samples for study outcome measures (GGT, %dCDT, 3α -diolG, and testosterone) will be obtained at visits 5 and 8 (mid-point and end of treatment). We chose biweekly medication monitoring visits during the treatment period in order to optimize tolerability and thereby enhance treatment retention.

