C.6.b.2. Areas assessed daily during the active treatment period: IVR will be used to collect daily ratings of alcohol subjective effects, mood, common triggers for drinking, past day drinking and medication usage. To facilitate the daily IVR interview, each patient will be provided with a wallet-sized interview guide with key term(s) for each interview question in the order in which it is presented by the system. A follow-along sheet detailing each question in the IVR phone call, including answer options, will also be given to subjects during the training session as a guide, and to assist the subject with the first few IVR call sessions.

a. *Daily drinking diary:* Every evening, as part of the IVR daily diary, patients will record their alcohol consumption as the number of standard drinks in each of four categories of alcoholic beverages: beer, wine, liquor and "other." Patients are asked to report separately drinking from yesterday and any drinking during the current day, up until the time of the IVR report. This allows us to examine lagged associations with mood and life event triggers. The time of the calls (5-10 PM) was chosen to balance a variety of patients work schedules and to reduce the potential for patients to have engaged in heavy drinking prior to making the calls. Once a patient is taught to complete the telephone interview, the time required each day is typically less than 5 minutes.

b. *Stimulating and Sedative Effects of Alcohol:* As an assessment of whether dutasteride moderates the intoxicating effects of alcohol, four probes will be included to assess how "buzzed, stimulated, calming or drowsy" patients felt who drank alcohol on the night prior or day of IVR.

c. *Daily mood:* Patients will be asked to rate as part of the daily IVR their mood using an adjective checklist. The checklist consists of 9 adjectives, one from each octant of the circumplex model of mood experience (Larsen and Diener 1992), with each adjective rated on a 5-point scale (0 = "not at all" to 4 = "extremely"). The octants measure unpleasant (*sad, angry*) and pleasant (*happy*) mood; high activated (*active*) and low activated (*tranquil*) mood; activated unpleasant (*nervous*) and activated pleasant (*enthusiastic*) mood; and unactivated unpleasant (*bored*) and unactivated pleasant (*relaxed*) mood.

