d. *Daily Events:* Participants will be asked whether they experienced a list of nine possible daily events (3 stressful, 3 pleasant, and 3 situations where someone might drink). These measures will be used to assess the influence of positive and negative events on drinking.

e. *Daily medication usage:* Using IVR, subjects will report daily medication use. Additionally, at each bi-weekly study visit, subjects will be asked by the study staff to indicate the number of study drug capsules taken each day. This method has been shown to be highly correlated with electronic monitoring of medication adherence (Feinn et al. 2003).

C.6.b.3. Areas assessed biweekly during the active treatment period and follow up visits:

a. *Alcohol use patterns:* The TLFB (Sobell and Sobell 1992) will be used to estimate drinking at intake, at each biweekly study visit during the active treatment period and at each of the two follow-up evaluations. This interview procedure will provide quantity/frequency of alcohol consumption data for each day during the period prior to the interview. We will also be collecting daily measures of alcohol consumption using IVR during the active treatment period because despite evidence of the reliability and validity of the TLFB when used by trained interviewers, the TLFB is less useful for detecting patterns of alcohol consumption that vary on a day-to-day basis (Carney et al. 1998; Searles et al. 2000). Daily IVR reports will also enable us to examine co-variation in daily mood and daily events with alcohol use in order to address whether dutasteride moderates associations between daily mood or daily events and drinking as our group has found using IVR methods for treatment with naltrexone (Kranzler et al. 2004; Armeli et al. 2006).

b. *Alcohol Craving:* The Penn Alcohol Craving Scale (PACS) is a 5-item self-report measure that includes questions regarding the frequency, intensity, and duration of craving over the past week as well (Flannery et al., 1999). The PACS has been shown to predict subsequent drinking during alcohol treatment trials (Flannery et al., 1999, 2003).

c. *Medication adverse effects:* Subjects will provide reports of side effects at each bi-weekly phone visit and study visit during the active treatment phase and 2-month follow-up visit using a list of adverse medication

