d. Alcohol outcome-expectancies will be assessed with 24 items from the Alcohol Effects Questionnaire [AEQ; (George et al. 1995)] probing 4 positive expectancy subscales (social and physical pleasure, aggression and power, social expressiveness, and relaxation and tension reduction) and 1 negative subscale (cognitive/physical impairment) to explore potential changes as a result of treatment with dutasteride. The AEQ will be administered at baseline and for those subjects who continue to drink again at midpoint, end of treatment and at the 4 and 6-month follow-up visits.

e. Integrity of the double blind: A Medication Questionnaire (MED-Q) will be completed by the subject at the end of treatment (or at the time of treatment discontinuation for subjects who do not complete the 12-week treatment period). It includes an indication of which medication group the subject believes to have been in, their level of confidence in that assessment and the reasons for coming to that conclusion.

C.6.b.5. Methodological Problems in Daily Monitoring:

i. Daily Recording: A research assistant will monitor the IVR call generated dataset regularly to review whether subjects are supplying daily responses and if not that problems and questions are promptly addressed. Subjects who fail to call in during the allotted time receive a computerized reminder call [which has been shown to increase the response rate by nearly 10% (Kranzler et al. 2004)]. Monetary incentives will be used to encourage subjects to make calls daily. Subjects will be paid \$1 for each telephone call completed and an additional \$3 for each week in which they complete all calls, to a maximum of \$120 (\$10 per week for 12 weeks). Although this is less than is paid for daily reporting in other studies, we have found that subjects in treatment studies do not require the same level of incentives to promote adherence to daily reporting as is the case for studies in which no other benefits accrue to participation.

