C.8.a.1. Safety: Safety will be analyzed using categorical outcomes, defined by the type and severity of adverse effects. Summary measures of adverse events (AEs) will be developed by organ system from the adverse event checklist and will be compared for patients receiving dutasteride or placebo using χ^2 analysis. Comparisons will be conducted on 1) the number of patients in each of the two groups who report AEs, 2) the number of patients in each of the two groups who report moderate-to-severe AEs, and 3) the number of patients in each group who discontinue treatment due to AEs. Individual AEs that occur in $\geq 5\%$ of patients in either medication condition will be examined using χ^2 analysis.

C.8.a.2. Efficacy: An important initial consideration will be to identify baseline differences between groups that may have occurred despite the use of urn randomization. The distribution of outcome data will also be examined prior to analysis, to determine the need for transformation and whether parametric analytic methods can be utilized. Successful outcome will be defined in terms of three primary dependent measures: SDs/week, HDDs/week, % of subjects with no HDDs, and % of subjects with non-hazardous drinking (no HDDs and SDs/week <15). Patients will be followed irrespective of whether they continue to receive treatment, so that analysis of both primary drinking measures and secondary outcomes will include all data available for the 12-week treatment period. Data for analyses of drinking outcomes during the 12-week treatment period will come from the daily IVR reports (missing IVR report days which will be coded as the larger of either 5 standard drinks (i.e. a HDD) or the IVR average daily use for the week reporting interval). Analysis of drinking for the 6-month follow-up period will be based on TLFB data collected at each follow-up visit. Secondary outcomes will include mean daily alcohol consumption, %dCDT levels (change relative to baseline), and severity of alcohol-related problems (as measured on the SIP and number of DSM-IV AD criteria).

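### Coding every missing IVR day as a heavy drinking day, without first using the drinking data already collected for that day, can fail a man who never drank heavily on both zero-HDD primary measures

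*Combined protocol and SAP*

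**What the plan says.** Section C.8.a.2 (Efficacy) fixes the source: "Data for analyses of drinking outcomes during the 12-week treatment period will come from the daily IVR reports". In the same sentence it deals with gaps: "missing IVR report days which will be coded as the larger of either 5 standard drinks (i.e. a HDD"). Where that week's mean reported intake is higher than 5 drinks, the mean is used instead. The HDD threshold comes from the Criteria for Study Participation, where men affirm a "treatment goal of no heavy drinking days (≥ 5 standard drinks in a day").

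The primary measures in C.8.a.2 include the percentage "of subjects with no HDDs, and % of subjects with non-hazardous drinking (no HDDs and SDs/week <15"). No window is given for these two yes/no measures beyond the general reference to the 12-week treatment period.

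Two other parts of the protocol collect drinking for days on which no call was made:

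- The daily drinking diary (C.6.b.2): "Patients are asked to report separately drinking from yesterday and any drinking during the current day, up until the time of the IVR report". A call therefore covers the whole of the previous day and part of the current one.
- The biweekly TLFB (C.6.b.3): "This interview procedure will provide quantity/frequency of alcohol consumption data for each day during the period prior to the interview". Section C.4.c says it tracks "daily alcohol consumption to augment IVR reports of alcohol use", and points to a section D.9.a.2 that is not in the document.

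C.8.a.2 then lists three conditions for checking robustness: all provided information, completers only, and HDD coding of missing days for men who do not complete treatment.

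**The concern.** The week's average can only raise the coded value above 5 drinks, so the code always produces an HDD. For an outcome that allows no HDD in 12 weeks, a single coded day decides the result, whatever the man reported on the other 83 days.

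Missed calls are common enough for this to matter. The pilot's 90% completion implies several per man over 12 weeks. Even with equal reporting in both arms, the rule would turn true responders into failures, compress both response rates towards zero and cost power on two primary measures. It would also add drinks and HDDs that never happened to the weekly counts.

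Much of this is avoidable. A skipped call need not leave a day without data, but the plan does not say which answers make an IVR day non-missing, and it does not bring in TLFB before the code applies. An analyst could defend either choice after seeing the data.

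**Working it through.** **Inputs from the documents.** 84 daily reports (12 weeks); pilot completion 90%, SD 10% (C.1.c); 80 completers per arm (C.8.b); HDD at 5 or more drinks; missing day = max(5, week's IVR average).

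**Assumed, because the documents do not give them.** True no-HDD rates of 20% vs 40%; pilot completion carries over to 12 weeks; completion varies between men as a beta distribution; reporting is unrelated to drinking; window of 84 days unless stated.

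**The plan's own figure.** For d = 0.45, two-sided α = 0.05 and 80 per arm, power is 0.81, against 80% stated in C.8.b. That figure reproduces, but it concerns a continuous effect size. C.8.b states no power for the yes/no measures.

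**Step 1: one abstinent man, one missing day.** The week's IVR average is 0, so max(5, 0) = 5 drinks = 1 HDD. The week's total of 5 is below 15, but the no-HDD condition fails, so he fails both measures over 12 weeks.

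**Step 2: missed calls.** 84 × 0.10 = 8.4 per man. If all are coded, an abstinent man is given 8.4/12 = 0.7 HDDs and 0.7 × 5 = 3.5 drinks per week.

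**Step 3: share of men with no missed call.** Mean 0.90 and SD 0.10 give Beta(7.2, 0.8), and E[p^84] = 0.130. The documents give only the mean and SD. Over means of 0.90–0.95 and SDs of 0.05–0.10 this share runs from 0.01 to 0.54.

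**Step 4: next-call fill.** Suppose either answer counts: the same-day answer or the next call's report on yesterday. A day is then lost only if two consecutive calls are missed. E[(1−p)²] = 0.01 + 0.01 = 0.02, so 84 × 0.02 = 1.7 days per man stay missing. With calls independent from day to day within a man, 0.587 of men are complete. If a full-day answer is required, each day needs the following call, and the complete share is again about 0.13.

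**Step 5: clustering.** Let adjacent calls within a man have correlation ρ. The no-gap share becomes E[p(p + ρ(1−p))^83]; the filled share is the chance of no two consecutive misses.

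**Step 6: power.** Exact enumeration of the two-sided pooled z test, 80 per arm, observed rates = complete share × (20%, 40%). With no gaps power is 0.80.

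| Setting | Share, no fill | Power | Share, next-call fill (either answer) | Power |
|---|---|---|---|---|
| 84 days, independent calls | 0.130 | 0.12 | 0.587 | 0.50 |
| 84 days, ρ = 0.3 | 0.168 | 0.14 | 0.351 | 0.30 |
| 84 days, ρ = 0.5 | 0.213 | 0.17 | 0.326 | 0.28 |
| 7 days, independent calls | 0.578 | 0.49 | 0.903 | 0.74 |
| 84 days, independent, responders at 95% (SD 5%) | 0.202 | 0.16 | 0.787 | 0.66 |
| 84 days, independent, responders at 98% (SD 2%) | 0.374 | 0.32 | 0.945 | 0.77 |

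In the first row, 0.130 × 20% = 2.6% and 0.130 × 40% = 5.2%. At the ends of the range in Step 3 (shares 0.01 and 0.54), power under the literal rule is about 0.00 and 0.45. Other true rates with about 80% power (10% vs 27%, 30% vs 52%, 40% vs 62%), with independent calls over 84 days, give 0.10–0.12 without the fill and 0.44–0.54 with it.

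**The case against.** **The rule is pre-stated and deliberately conservative.** IVR is preferred for good reason: C.6.b.5 reports that men under-report on TLFB relative to IVR, and C.6.b.3 says TLFB is less useful for day-to-day variation. This stands as a reason to keep IVR first and to show an IVR-only result. It does not justify ignoring a man's own next-day IVR answer, or assigning 5 drinks to a date for which a TLFB value exists.

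**Gaps are limited.** C.6.b.5 says "Subjects who fail to call in during the allotted time receive a computerized reminder call", and calls are paid. These measures reduce gaps but set no rule for those that remain, and the pilot's 90% still implies 8.4 missed calls in 84.

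**The window may be weekly.** The model uses treatment week, and the non-hazardous measure contains a weekly drink limit. This stands: no window is stated for the yes/no measures, and with a one-week window the loss is much smaller.

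**The size rests on assumptions.** This also stands. The true rates were chosen to give about 80% power, and the beta shape and day-to-day independence are not documented. Clustering leaves the loss under the literal rule in place but removes most of the benefit of the next-call fill.

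**Stronger readings that the documents do not support.** A reader might infer that every missed call fails a man; the plan codes missing report days, and does not say whether a next-day answer prevents a day from being missing. A reader might infer bias between arms; no arm difference in reporting is documented, and pilot dropout was 2 placebo and 1 active. A reader might also infer that the missing-day rule and the three robustness conditions contradict each other. They can be read as a main rule with checks around it. What is missing is a named main analysis and a statement of how a man with gaps is classed on the yes/no measures.

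**Conclusion.** The point holds in this form. The code always yields an HDD. Over a 12-week window one coded day fails a man on both zero-HDD primary measures, and the plan does not use data it already collects before applying the code. This follows from the text and needs no assumption beyond the window.

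The size is illustrative. At pilot reporting levels and an 84-day window, power on a 20% vs 40% difference falls from 0.80 to about 0.12–0.17. A next-call fill brings it back to about 0.50 at best, and to 0.28–0.30 if missed calls cluster, so TLFB is needed for much of the recovery. The loss shrinks with a shorter window or better reporting by responders, and vanishes if they report completely. It should be fixed before unblinding. It does not show that the trial as a whole is underpowered.

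**What to change.** Before unblinding, amend C.8.a.2 as follows:

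1. Define a missing IVR day, including whether a day with only a same-day answer up to the time of the call counts as observed.
2. State the window for the two zero-HDD measures and how a man with gaps is classed.
3. For these measures and the weekly counts, fill a missing day first from the next call's report on yesterday, then from the TLFB for that date. Apply the 5-drink code only to days missing on both sources, and flag filled days.
4. Name one main analysis, say that the three listed conditions are robustness runs around it, and keep the IVR-only rule (missing = HDD) as a sensitivity analysis.
5. Report missing and filled days by arm.

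Leaving days missing in the mixed model, or multiply imputing responder status, can be added as optional sensitivity analyses. Both rely on missing at random, which is doubtful if calls are skipped after drinking.

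The cost is plan wording and a merge of data already collected. The drawback is TLFB under-reporting: an arm with more TLFB-filled days could look better. Show the IVR-only result alongside, and compare the two sources on days when both exist. TLFB cannot fill days for men who stop attending and give no later interview; for them the code still applies.
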